5.1.2 Secondary Endpoints Definitions

Objective Response per RECIST 1.1 (OR):

OR is defined as a partial response (PR) or complete response (CR) per RECIST 1.1, confirmed by a repeat assessment at least 4 weeks later. Subjects who do not experience a confirmed PR/CR or do not have any follow-up tumor assessments will be regarded as non-responders. This endpoint applies only to subjects with measurable baseline disease per RECIST 1.1.

Details for derivation of Objective Response per RECIST 1.1 are described in [Appendix B](#).

Overall Survival:

Overall survival is defined as the time from the date of Study Day 1 until death due to any cause:

OS time (Days) = date of death - Study Day 1 + 1.

Any subject not known to have died at the time of analysis will be censored based on the last recorded date on which the subject was alive.

PSA Progression:

PSA progression is defined as per PCWG3.

- After a decline in PSA from baseline to post-treatment, a PSA increase of $\geq 25\%$ and ≥ 2 ng/mL above the nadir (the lowest value up to the assessed visit date). This PSA progression must be confirmed by a second consecutive value ≥ 3 weeks later.
- No decline in PSA from baseline, a PSA increase of $\geq 25\%$ and ≥ 2 ng/mL from baseline at or beyond 12 weeks after treatment initiation.

Radiographic Progression:

A radiographic progression occurs if either of the following occurs:

- Progressive disease per RECIST 1.1 occurs.
- Bone disease progression as per PCWG3 occurs. Bone disease progression for the first post-treatment bone scan (e.g. Week 8) showing two or more additional lesions relative to screening/baseline must be confirmed by the next bone scan (e.g. Week 16) showing two or more additional lesions relative to first post-treatment bone scan (e.g. Week 8) at least 6 weeks later. Bone disease progression for scans after the first post-treatment scan (e.g. Week 16) showing two or more additional lesions relative to the first post-treatment bone scan (e.g. Week 8) can be confirmed by second scan showing persistence of the additional lesion relative to the first post-treatment scan (e.g. Week 8) at least 6 weeks later.

PSA Progression-free Survival (PSA PFS):

PSA PFS is defined as the interval from Study Day 1 to the earlier of a PSA progression or death from any cause; otherwise, PSA PFS is censored on the date of the last PSA measurement. If a subject has no baseline or post-baseline PSA measurement and a vital status of alive or unknown, PSA PFS will be censored at Study Day 1.

More details about censoring rules are included in [Appendix D](#).

Radiographic Progression-free Survival (rPFS):

rPFS is defined as the interval from Study Day 1 to the earlier of a radiographic progression or death from any cause; otherwise, rPFS is censored based on the criteria in [Appendix D](#).

PSA Response (PSA 30):

A PSA response (PSA30) is defined as a $\geq 30\%$ decrease below baseline confirmed by a second consecutive value obtained 3 or more weeks later. An increase in PSA in the first 12 weeks does not preclude a response thereafter. Only subjects with measurable (i.e., > 0) baseline PSA will be evaluated for PSA response.

PSA Response (PSA 50):

A PSA response (PSA50) is defined as a $\geq 50\%$ decrease below baseline confirmed by a second consecutive value obtained 3 or more weeks later. An increase in PSA in the first 12 weeks does not preclude a response thereafter. Only subjects with measurable (i.e., > 0) baseline PSA will be evaluated for PSA response.

PSA Response (PSA 70):

A PSA response (PSA70) is defined as a $\geq 70\%$ decrease below baseline confirmed by a second consecutive value obtained 3 or more weeks later. An increase in PSA in the first 12 weeks does not preclude a response thereafter. Only subjects with measurable (i.e., > 0) baseline PSA will be evaluated for PSA response.

PSA Response (PSA 90):

A PSA response (PSA90) is defined as a $\geq 90\%$ decrease below baseline confirmed by a second consecutive value obtained 3 or more weeks later. An increase in PSA in the first 12 weeks does not preclude a response thereafter. Only subjects with measurable (i.e., > 0) baseline PSA will be evaluated for PSA response.

Time to PSA Progression:

Time to PSA progression is defined as the interval from Study Day 1 to PSA progression; otherwise, time to PSA progression is censored based on the criteria in [Appendix D](#).

Time to Radiographic Progression:

Time to radiographic progression is defined as the interval from Study Day 1 to radiographic progression; otherwise, time to radiographic progression is censored based on the criteria in [Appendix D](#).

Duration of Response (DOR) per RECIST 1.1:

DOR is defined as the time from the date of an initial objective response per RECIST 1.1, which was subsequently confirmed, to the earlier of soft-tissue progression per RECIST 1.1 or death. Subjects who have not ended their response at the time of analysis will have DOR censored at their last evaluable tumor assessment by CT/MRI scan. This endpoint only applies to subjects with an objective response per RECIST 1.1.

Duration of PSA Response (PSA DOR):

PSA DOR is defined as the time from the date of initial PSA response (PSA 50), which was subsequently confirmed, to the earlier of PSA progression or death. Subjects who have not ended their response at the time of analysis will have PSA DOR censored on the date of their last PSA measurement. The endpoint only applies to subjects with a PSA response (PSA 50).

Details about the censoring rules are included in [Appendix D](#).

Time to Symptomatic Skeletal Events:

Time to SSE is defined as time from Study Day 1 to the first SSE. Otherwise, SSE is censored at the last dose date of investigational product (AMG 340) or end of safety follow-up date, whichever is later.

A Symptomatic Skeletal Event (SSE) is defined as any of the following which is collected on the **Adverse Events** eCRF:

For Part A of the study, a list of preferred terms will be identified at the time of analysis for what constitutes an SSE.

For Part B: there is a separate event categories to identify them

- A symptomatic fracture which is any adverse event of fracture (ankle, hip, spinal, wrist or other) per CTCAE version 5.0.
- Radiation or surgery to bone.
- Spinal cord compression.

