a  $\pm$  7 days. Timing is based on first dose of AMG 340 (cycle 1 day 1).  
b Responses (PR and CR) require confirmation by a repeat consecutive CT/MRI assessment no sooner than 4 weeks after the first detection of radiographical response.  
c Per PCWG3 recommendations, the first post-treatment bone scan (at C3D1) will be used as the baseline scan with which all future bone scans are compared. To confirm disease progression by bone scan, a second bone scan must be performed at least 6 weeks after the 2nd of the 2 lesions is noted ("2+2" rule set).  
d Radiologic imaging (CT/MRI) and bone scan scintigraphy are required at the EOT or SFU visit if the subject has not had these imaging assessments performed within 6 weeks of the visit. For PET/CT imaging [REDACTED] and F-FDG), every effort should be made to acquire PET/CT scans at the EOT or SFU visit, or prior to initiation of other therapy if the subject has not had PET/CT imaging performed within 8 weeks of the visit.  
e For subjects who discontinued treatment for any reason other than radiographic disease progression, every effort should be made to perform radiographic imaging (CT/MRI/bone scan) of the chest, abdomen, pelvis, and all other known sites of disease every 3 months until documentation of radiographic disease progression per PCWG3, clinical progression, biochemical progression, start of new anticancer therapy, or up to 3 years after the first dose of study treatment.  
f Blood samples or tumor biopsy must not be collected until at least 24 hours after a PET/CT scan, or at least 60 hours (or 2.5 days) following a bone scintigraphy scan.  
g Subjects off-treatment for reasons other than disease progression or withdrawal of consent should continue with disease response assessments every 12 weeks ( $\pm$  7 days) until documented disease progression, initiation of subsequent anticancer therapy, or withdrawal.

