#### **8.1.4 Long-term/Survival Follow-up**

Subjects will be followed for survival and/or the commencement of subsequent cancer therapy via clinic visits, telephone, or chart review call every 6 months from the last SFU

visit for up to a maximum of 3 years. All procedures to be completed during long-term/survival follow-up are indicated in the Schedule of Activities (Section 1.3).

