Appendix D. Censoring Rules

Censoring rules for radiographic PFS (rPFS):

Situation up to DCO/EOS	Date of Event or Censoring	Outcome
No evaluable post-baseline or on-study disease assessment; on study without disease progression or death recorded	Date of the first dose of Investigational product (AMG 340)	Censored
PD prior to new anti-cancer therapy	Date of PD	Event
No PD, but death recorded without new anti-cancer therapy	Date of Death	Event
Start of new anti-cancer therapy prior to PD or death, or prior to any other disease assessment if there is no PD or death recorded	Date of last evaluable radiographic tumor assessment prior to the start of new anti-cancer therapy	Censored
No PD or death, no new anti-cancer therapy	Date of last evaluable radiographic tumor assessment	Censored

DCO: Data Cut-off; EOS: End of Study; PD: Progressive Disease

Censoring rules for PSA PFS:

Situation up to DCO/EOS	Date of Event or Censoring	Outcome
No evaluable post-baseline or on-study PSA assessment (on study without PSA progression or death); no evaluable baseline PSA assessment	Date of the first dose of Investigational product (AMG 340)	Censored
PSA Progression	Date of PSA Progression	Event
Death	Date of Death	Event

All other scenarios	Date of last PSA assessment.	Censored
---------------------	------------------------------	----------

DCO: Data Cut-off; EOS: End of Study; PSA: Prostate Specific Antigen

Censoring rules for Time to PSA Progression:

Situation up to DCO/EOS	Date of Event or Censoring	Outcome
No evaluable baseline or post-baseline or on-study PSA assessment	Date of the first dose of Investigational product (AMG 340)	Censored
PSA Progression	Date of PSA Progression	Event
All other scenarios	Date of last PSA assessment	Censored

DCO: Data Cut-off; EOS: End of Study; PSA: Prostate Specific Antigen

Censoring rules for Time to Radiographic Progression:

Situation up to DCO/EOS	Date of Event or Censoring	Outcome
No evaluable post-baseline or on-study disease assessment; on study without progressive disease or death	Date of the first dose of Investigational product (AMG 340)	Censored
PD prior to new anti-cancer therapy	Date of PD	Event
No PD, but death recorded without new anti-cancer therapy	Date of last evaluable radiographic tumor assessment	Censored

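### PSA PFS and PSA duration of response count deaths at any time and never censor at new anticancer therapy, unlike the radiographic endpoints, which inflates mainly the tail of the PSA PFS curve

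*SAP*

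**What the plan says.** **Events and censoring for the PSA endpoints.** SAP 5.1.2: "PSA PFS is defined as the interval from Study Day 1 to the earlier of a PSA progression or death from any cause". For a subject with neither event it sets the following rule: "otherwise, PSA PFS is censored on the date of the last PSA measurement". For PSA DOR the event is PSA progression or death, and "Subjects who have not ended their response at the time of analysis will have PSA DOR censored on the date of their last PSA measurement". In Appendix D, the table for PSA PFS has four rows: no evaluable PSA, PSA progression, death, and everything else (censored at the last PSA). The PSA DOR table has the last three. Neither has a row for new anticancer therapy or a limit on the gap between the last PSA and death. The table for time to PSA progression also lacks a new-therapy row, but it does not count deaths.

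**Events and censoring for the radiographic endpoints.** In the same appendix, a subject who starts new therapy before progression or death is censored for rPFS and time to radiographic progression at the "Date of last evaluable radiographic tumor assessment prior to the start of new anti-cancer therapy". RECIST DOR has the same rule, based on CT/MRI.

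**When PSA is measured.** Protocol Table 1-3 marks PSA at screening, day 1 of each cycle, end of treatment (EOT) and safety follow-up (SFU), and marks nothing under survival follow-up. Footnote g continues off-treatment disease assessments every 12 weeks, but only "until documented disease progression, initiation of subsequent anticancer therapy, or withdrawal".

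**When deaths are collected.** Protocol 8.1.4: "Subjects will be followed for survival and/or the commencement of subsequent cancer therapy via clinic visits, telephone, or chart review call every 6 months", for at most 3 years from the last SFU visit. The final analysis follows the end of study for all subjects (SAP 7.3). If Part B does not go ahead, the primary analysis is merged into it (SAP 7.2).

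**The concern.** Once PSA measurement has stopped, two subjects with identical PSA data are treated differently. The one who is alive at analysis leaves the risk set at his last PSA. The one who later dies stays in it until death, and the time between is credited as free of PSA progression. Membership of the risk set then depends on a future event, which the Kaplan-Meier method does not allow.

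Much of that time may be spent on another drug, so the late part of the curve partly describes survival on later therapy. The PSA endpoints are also on a different footing from rPFS: new therapy ends follow-up for one and not for the other, and the SAP gives no reason for the difference.

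The PSA progression definition can add to this. A subject whose PSA never declines can meet it only "from baseline at or beyond 12 weeks after treatment initiation". If he stops early for radiographic progression and starts new therapy before week 12, PSA progression may never be recorded and his event becomes his death.

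**Working it through.** The documents give no event count, power or expected value for PSA PFS or PSA DOR, so there is no planned figure to reproduce. The rules are compared first. The size is then illustrated under assumptions.

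**1. Rules side by side (SAP Appendix D)**

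| Situation | PSA PFS, PSA DOR | rPFS, RECIST DOR |
|---|---|---|
| Death, no new therapy | Event at death | Event at death |
| Death after new therapy | Event at death | Censored before new therapy |
| Alive, new therapy started | Censored at last PSA, even if after new therapy | Censored before new therapy |

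**2. Longest gap.** If the last PSA is at SFU, a counted death can come up to about 36 months later.

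**3. Constructed example.** A subject stops at month 4 for radiographic progression without PSA progression. His last PSA is at EOT in month 4, he starts new therapy in month 5, and he dies in month 24. His PSA PFS is an event at 24 months, of which 24 - 4 = 20 months are unmeasured. His rPFS is an event at month 4. A subject with the same history who is alive at analysis is censored for PSA PFS at month 4.

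**4. Size. All inputs are assumptions.** Independent exponential times with medians of 4 months (PSA progression), 10 (OS) and 3 (stopping treatment for other reasons). PSA is observed until 1 or 3 months after stopping, and deaths for 36 months beyond that.

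True PSA PFS in closed form is S(t) = 2^-(t/4 + t/10):
- S(6) = 2^-2.1 = 0.233
- S(12) = 2^-4.2 = 0.054
- median = 1/(1/4 + 1/10) = 2.86 months

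Simulated under the SAP rule:

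| | Last PSA 1 month after stop | Last PSA 3 months after stop | True |
|---|---|---|---|
| 6 months | 0.339 | 0.272 | 0.23 |
| 12 months | 0.189 | 0.139 | 0.05 |
| Median (months) | 3.17 | 2.86 | 2.86 |

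The bias is small at the median and large in the tail.

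**5. Longer OS and earlier last PSA.** A second set of nine assumed scenarios used OS medians of 12 or 18 months, PSA progression 3-6, stopping 2-6, last PSA at EOT and new therapy 1 month after stopping. The median under the SAP rule was 3.5-6.7 months against a true 2.4-4.5. Scenario by scenario the shift ran from 0.5 (3.5 against 3.0) to 2.2 months (6.7 against 4.5). Deaths after new therapy were 28-51% of all PSA PFS events, with a median gap of 11-14 months from the last PSA.

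**6. Does the new-therapy row help?** In the setting of step 4, with new therapy taken to start when PSA measurement stops, censoring there returns a 12-month value of 5%, the true value. In the scenarios of step 5 the 12-month value falls from 0.19-0.36 to 0.02-0.15, against a true 0.03-0.16. With correlated times (Gaussian copula 0.5, last PSA 1 month after stopping), the 12-month value is 23.1% under the SAP rule, 16.5% with the new-therapy rule and 9.5% in truth. The new-therapy rule is closer but still too high.

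**The case against.** Several points on the other side stand.

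- **The reported statistic is mostly the median.** SAP Table 9-1 names the median and other percentiles for PSA PFS, and its only landmark endpoint is 6-month rPFS. In the setting of step 4 the median moves 0-0.3 months. A reader might infer that the headline PSA PFS figure is badly inflated; that setting does not support this. Protocol 9.4.2.2 does, however, plan Kaplan-Meier rates and curves, and the tail is visible there.
- **rPFS also counts late deaths.** Where no new therapy was given, the rPFS and RECIST DOR tables make a death an event at any gap. A reader might infer that the radiographic rules limit the gap and only the PSA rules do not. That is wrong: the difference lies in the new-therapy row alone. Counting death in a PFS endpoint is standard and is not the fault here.
- **A 6-week death window would not fit the schedule.** Six weeks is two PSA intervals only on treatment. EOT (within 30 days of last dose) and SFU (about 90 days) lie about 60 days apart, and footnote g gives 12 weeks. A subject who missed no visit could die 7-8 weeks after his EOT PSA and be wrongly censored.
- **The week-12 case is narrow.** SFU normally provides a PSA after week 12 even for a subject who stops at week 6. The case needs new therapy early enough to bring SFU forward.
- **Consequence is limited.** No test or decision rests on these endpoints. PSA DOR gets Kaplan-Meier estimates only with more than 10 PSA50 responders. OS and time to PSA progression are reported separately.

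One point does not stand. Footnote g might extend PSA beyond SFU for subjects off treatment without progression, but it ends at progression or new therapy, which is where the problem arises.

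**Conclusion.** The concern holds as a difference in rules with a real effect on the tail. PSA PFS and PSA DOR treat death after new therapy as an event although PSA is no longer measured, while the three radiographic tables censor at new therapy. Under the assumptions of step 4, 12-month PSA PFS is 14-19% against a true 5%, and the median is little affected. Longer OS, an earlier last PSA or correlated times shift the median more. These figures illustrate the size and are not forecasts for this trial.

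A reader might go further and infer that gaps of years are typical, or that both Kaplan-Meier curves will certainly be biased. The documents do not support either. Three years is the cap on survival follow-up, not the usual gap, and the PSA DOR curve may never be produced. The change is worth making, but it affects secondary, descriptive results only.

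**What to change.** In SAP Appendix D:

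1. Add to the tables for PSA PFS, PSA DOR and time to PSA progression the row already used for rPFS: if new anticancer therapy starts first, censor at the last PSA before it.
2. For PSA PFS and PSA DOR, count a death as an event only if no new anticancer therapy was started. Align the definitions in SAP 5.1.2.
3. Keep the present rule as a sensitivity analysis.
4. Do not add a fixed 6-week death window. If a gap limit is wanted, base it on two consecutive missed assessments under the schedule in force at the time (3-weekly on treatment; EOT/SFU or 12-weekly off treatment), and apply it to rPFS as well.

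The cost is SAP wording and a few lines of programming, with no change to visits or data collection, since the start of subsequent therapy is already followed. The downside is more censoring. Part of it will be informative, because subjects who change therapy are likely to be doing worse, so some upward bias remains and the report should say so.

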Window		±1h	±1h	±1d	±1h	±1h	±1h	±1d	±1h	±1h	±1d	±1d	±1d	±1d	±1d	±1d	±1d	±1d	±1d	±1d	±1d	+7d	±7d		
Disease Assessments e, h		Refer to Table 1-3																							
Adverse event collection i	X	Recorded from the time of consent through SFU n																					X		
Serious adverse event collection m		Continuously throughout the study																							
Concomitant medications/therapy p		Recorded within 2 weeks from the first dose of study drug through SFU n																							
Survival																							X		

ADA = antidrug antibody; D = day; D/C = discharge; DLT = dose-limiting toxicity; ECG = electrocardiogram; ECHO = echocardiogram; ECOG = Eastern Cooperative Oncology Group; EOT = end-of-treatment; FU = follow-up; LTFU = long-term follow-up; PK = pharmacokinetic(s); SFU = safety follow-up; T1/2 = terminal half-life; UNS = unscheduled; W = week.

Note: Every effort should be made to keep the Schedule of Events on time for each subject.

a An unscheduled visit may occur at any time during the study. Study activities shown will be performed at the investigator's discretion.

b The EOT visit should occur within 30 days after the last dose of AMG 340. If an alternate therapy will be initiated during this period, the EOT visit should be conducted prior to the first dose of alternate therapy.

c Subjects will be admitted for 48 hours **after the infusion on C1D1 and, if implemented, after a second priming dose on C1D5**. If priming doses are **implemented**, subjects will also be admitted for 48 hours on C1D8 (note that a second priming dose may be implemented based on emerging data).

d Vital sign measurements include measurements of diastolic and systolic blood pressure, heart rate, respiratory rate, and temperature. On day 1 dosing, vital signs should be measured prior to study drug administration (up to 10 minutes before), 30 ± 10 minutes after initiation of study drug administration, at completion of study drug administration (±10 minutes), and 1 hour ± 10 minutes after completion of study drug administration; on C1D1 and on **C1D5 and C1D8**, if priming doses have been implemented, vital signs should also be measured 3, 6, and 9 hours ± 10 minutes after completion of study drug administration. Vital signs should be taken after 5 minutes of sitting or lying down.

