##### **8.4.6.1 Time Period and Frequency for Collecting and Reporting Safety Event Information**

###### **8.4.6.1.1 Adverse Events**

The adverse event grading scale to be used for this study will be the CTCAE and is described in Section [11.4](#). CRS, which will be graded using the criteria referenced in the publication by Lee et al (2019) (see Section [11.10](#)) and TLS, which will be graded according to the Cairo Bishop criteria referenced in the publication by Coiffier et al (2008) (see Section [11.11](#)), and ICANS will be using the criteria referenced in the publication by Lee et al (2019) (see Section [6.2.1.6.1.1](#)).

The investigator is responsible for ensuring that all adverse events observed by the investigator or reported by the subject that occur from the time of consent through the safety follow-up visit 90 (+ 7) days after the last dose of study drug, are reported using

the Events CRF. For subjects that start a new line of therapy before the 90 (+ 7) day follow-up visit, all adverse events should be collected and reported through 30 days post last dose of investigational product/protocol-required therapies or until the subject begins a new line of therapy, whichever occurs later.

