#### **8.4.6.1.3      Serious Adverse Events After the Protocol-Required Reporting Period**

During the long-term follow-up period if the investigator becomes aware of serious adverse events (regardless of causality) after the protocol-required reporting period (as defined in Section 8.4.6.1.2) is complete, then these serious adverse events will be reported to Amgen. The investigator will report serious adverse events to Amgen immediately and no later than 24 hours following the investigator's awareness of the event on the Events CRF.

There is no requirement to actively monitor study subjects after the study has ended with regards to study subjects treated by the investigator. However, if the investigator becomes aware of serious adverse events suspected to be related to investigational product, then these serious adverse events will be reported to Amgen immediately and no later than 24 hours following the investigator's awareness of the event.

Serious adverse events reported **after the end of the study** will be captured within the safety database as clinical trial cases and handled accordingly based on relationship to investigational product.

If further safety related data is needed to fulfill any regulatory reporting requirements for a reportable event, then additional information may need to be collected from the subject's records after the subject ends the study.

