5.1 Study Endpoints

5.1.1 Primary Endpoints Definitions

Treatment-Emergent Adverse Event (TEAE):

Events categorized as Adverse Events (AEs) starting on or after the first dose of AMG 340 as determined by “Did event start before first dose of AMG 340” equal to “No” or missing on the **Adverse Events** eCRF and up to and including 90 days after the last dose of AMG 340 (however, if subject start a new line of therapy before 90 days follow-up visit, safety follow-up will be performed through 30 days post last dose of AMG 340 or until subject begins a new line of therapy, whichever occurs later) excluding events reported after End of Study Date. **Events that are directly related to metastatic castrate-resistant prostate carcinoma cancer or disease progression (including, but not limited to, preferred terms “prostate cancer”, “progression of prostate cancer”, “prostate cancer metastatic”, “disease progression” etc.) will be excluded from TEAE analysis.**

Treatment-Related Adverse Event (TRAЕ):

A treatment-related AE is any treatment-emergent AE with the relationship flag on the **Adverse Events** eCRF indicating there is a reasonable possibility that the event may have been caused by AMG 340. In the unlikely event that the relationship is missing, the treatment-emergent event will be considered treatment-related and documented in a footnote of the treatment-related summary.

Dose-limiting Toxicities (DLTs):

Investigators determine whether a TEAE qualifies as a DLT per the definition described in protocol section 6.2.1.4.1. For an adverse event to qualify as DLT, the start date must be within 21 days from the date of first dose of AMG 340.

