5.2 Study Time Points

Study Day 1:

Study Day 1 is defined as the date of the first dose of the AMG 340 administered to the subject.

End of Treatment:

End of treatment is defined as the date the decision was made to end of AMG 340 as recorded on the End of Treatment Status eCRF page.

End of Study for Individual Subject:

End of study for individual subject is defined as the date of the subject last completed a protocol-specified procedure. The date will be recorded on the End of Study eCRF page.

End of Study:

End of study date is defined as the date when the last subject across all sites is assessed or receives an intervention for evaluation in the study (i.e., Last subject last visit), following any additional parts in the study (e.g., long-term follow-up), as applicable.

Safety follow-up Visit:

Safety follow-up visit is defined as upon permanent discontinuation from the study treatment for any reason, a safety follow-up visit will be performed approximately 90 (+7) days after the end of the last dose of AMG 340 and/or product required therapies. However if subject starts a new line of therapy before 90 (+7) days follow-up visit, safety follow-up will be performed through 30 days post last dose of AMG 340 or until the subject begins a new line of therapy, whichever occurs later.

Long-term follow-up Visit:

Subjects will be followed for survival and/or the commencement of subsequent therapy via clinic visit, telephone, or chart review call every 6 months from the SFU visit for up to a maximum 3 years.

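### Time to SSE has no cut-off for events but censors event-free subjects at safety follow-up, so late serious SSEs bias the later Kaplan-Meier curve downward

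*SAP*

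**What the plan says.** **Event.** SAP 5.1.2: "Time to SSE is defined as time from Study Day 1 to the first SSE". No latest onset date is given, and the event is not limited to treatment-emergent events.

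**Censoring.** The same paragraph: "SSE is censored at the last dose date of investigational product (AMG 340) or end of safety follow-up date, whichever is later".

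**Source.** SSEs are identified from data "which is collected on the Adverse Events eCRF".

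**What reaches that form, and when.** Protocol 8.4.6.1.1 has investigators report all adverse events that "occur from the time of consent through the safety follow-up visit 90 (+ 7) days after the last dose of study drug" (a shorter period can apply if a new line of therapy starts). Reporting of serious events does not stop there. Protocol 8.4.6.1.3 requires a report on the Events CRF "if the investigator becomes aware of serious adverse events (regardless of causality) after the protocol-required reporting period", and the Schedule of Activities shows serious adverse event collection as "Continuously throughout the study". Long-term contact runs "every 6 months from the SFU visit for up to a maximum 3 years" (SAP 5.2).

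**Is a cut-off supplied elsewhere?** No. SAP Appendix D has censoring tables for rPFS, PSA PFS, both times to progression and both durations of response, but none for SSE. SAP 5.1.1 limits treatment-emergent adverse events to those "up to and including 90 days after the last dose of AMG 340" (with a variant for new therapy), but nothing applies that limit to SSEs.

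**Analysis.** SAP Table 9-1 plans descriptive statistics. A Kaplan-Meier median and other percentiles are added only if more than 10 subjects have an SSE. That count has no cut-off either.

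**The concern.** Kaplan-Meier estimation needs each subject's time at risk to end for reasons unrelated to a future event. Here, for any subject past SFU, the rule itself breaks that condition. If a serious SSE is later reported, the subject stays in the risk set until that date. If not, the subject is removed at SFU, even when known to be alive and followed for just as long. Late events are then divided by a risk set that has lost many event-free members. The late part of the curve falls too fast, and any percentile read from it comes too early. The SAP covers the final analysis, after all subjects have ended the study, so late reports will be in the database by then.

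**Working it through.** The plan gives no SSE rate, event count or precision, so there is no SSE figure to reproduce.

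**Step 1: the mechanism.** At the time of a late SSE, let
- m = event-free subjects who have not yet reached their own SFU date,
- k = subjects past SFU kept at risk because they have an SSE reported now or later,
- c = subjects past SFU, alive and event-free, already censored.

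The rule multiplies the curve by 1 − 1/(m + k). With follow-up treated alike, the factor would be 1 − 1/(m + k + c). The first is smaller whenever c > 0. If m = 0 and k = 1 it is 1 − 1/1 = 0, and the curve ends at zero.

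**Step 2: inputs.**
- From the documents: up to 60 subjects in Part A and about 100 in total; SFU about 3 months after last dose; long-term follow-up up to 36 months after SFU.
- Assumed: exponential times; SSE hazard 3% per month; mean treatment 4 months; median survival 14 months; a share q of first SSEs after SFU that reach the form. The documents give none of these.

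**Step 3: true values.** S(t) = exp(−0.03t). S(6) = exp(−0.18) = 0.835. S(12) = exp(−0.36) = 0.698.

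**Step 4: simulated Kaplan-Meier estimate at 12 months, N = 60.**

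| Late capture q | 12-month estimate | Difference from true 70% |
|---|---|---|
| 0% (same as a matched cut-off) | 70% | 0 |
| 10% | 67% | −3 points |
| 25% | 64% | −6 points |
| 50% | about 60% | about −10 points |

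The 6-month estimate moves by about 2 points or less.

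**Step 5: other assumptions.** With median time to SSE 12, 18 or 30 months, median treatment 3 or 6 months and N = 60 or 100, the 12-month bias is 0.01 to 0.03 downward at q = 10% and 0.06 to 0.13 at q = 100%. With events cut at SFU, the 12-month estimate is within 0.01 of the truth in every setting.

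**Step 6: percentiles, which are the planned output.** With N = 100, true median 18 months and median treatment 6 months, the more-than-10 condition is met in essentially every run. The typical estimated median is 18.5, 17.3, 16.0, 15.1 and 13.9 months at q = 0%, 10%, 25%, 50% and 100%.

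**Step 7: the more-than-10 condition.** At N = 60 and 1.5% per month, more than 10 subjects have an SSE in about 1% of runs with a matched cut-off, and in 8%, 28% and 55% at 25%, 50% and 75% capture. At 3% per month it is met in 73% to 99% of runs over the same capture range. Late events therefore help trigger the curve that they distort.

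**The case against.** The best defence is that a common cut-off was probably intended. The censoring date coincides with the end of routine adverse event collection, and the long-term contact is for survival and subsequent therapy, not for skeletal events. After SFU, only serious events that the investigator happens to learn of are reported. A non-serious fracture would normally be missed. Radiation or surgery to bone is a procedure, which Protocol Appendix 4 says is not itself an adverse event, so its late capture is doubtful. If no late SSE is recorded, there is no bias. At a low SSE rate with 60 subjects, the Kaplan-Meier analysis would often not be run at all. Time to SSE has no hypothesis, test or decision rule.

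All of that stands as a limit on size and priority. It does not remove the point. The cut-off is not written, a programmer following the text would count a late serious cord compression, and the SAP shows elsewhere that it can state a window when it wants one.

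Two stronger readings are tempting, and the documents support neither.
- A reader might infer that after SFU only subjects with an event remain at risk, so that the curve must run to zero. SFU dates differ between subjects, and those still on treatment or in SFU stay at risk without an event. The risk set holds only event subjects after the last event-free subject has been censored. How often the curve ends at zero depends on the unknown capture share. In the Step 5 settings it does so in 9% to 25% of runs even with matched cut-offs, and in 30% to 64% at 10% capture.
- A reader might infer that every SSE at any time is counted. Late capture is confined to serious events that come to the investigator's attention.

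**Conclusion.** The rule is wrong as written: events are open-ended and event-free time is not. The direction is certain if any late serious SSE is recorded, because the late curve and its percentiles are then biased downward. The size is not known. At 12 months it is about 3 points at 10% capture and about 10 points at 50%, under the assumed 3% monthly hazard, 4-month mean treatment and 14-month median survival. It is nil with no late capture and negligible at 6 months. Estimates at 24 months rest on very few subjects and are unstable even without this defect, so they should not carry the argument.

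One small inference is involved: that the SAP's Adverse Events eCRF is the protocol's Events CRF. The serious adverse event form instructions in Protocol Appendix 4 equate the AE Summary CRF with the Events CRF, which supports it.

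Priority is low to moderate.

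**What to change.** Add to SAP 5.1.2: only SSEs with onset on or before the later of the last AMG 340 dose and the end of safety follow-up count as events, both for the Kaplan-Meier analysis and for the more-than-10-subject condition; a subject whose first SSE is later is censored at that date, and the event is listed.

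The cost is one sentence. A few late SSEs move from the curve to a listing. No new data are needed, and nothing changes if no late SSE occurs. The alternative is to collect SSEs actively in long-term follow-up and censor at the last SSE assessment. That would use the longer follow-up, but it needs a protocol change and added data collection.
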